### **5.18 Salvage Therapy**

Patients who discontinue treatment on this study may receive other experimental treatments or be offered studies if felt to be appropriate.

## 6. Study Procedures

### 6.1 Screening

Demographic data, clinical history, response to previous treatments, functional status, imaging and histology results to date will be ascertained at baseline on a standard case report form (CRF). Patients will be eligible irrespective of k-ras mutation status.

The following screening procedures will be performed within up to 28 days prior to the start of treatment on study, unless otherwise stated:

- Patient signature on informed consent form (up to 28 days prior to treatment)
- Medical history including confirmation of histological diagnosis, history of other concomitant illnesses
- Demographics (including age, sex, and race)
- Physical examination including examination of major body systems, ECOG performance status, body weight, height (screening only), and vital signs (temperature, blood pressure, heart rate)
- Haematology performed within 7 days from treatment start
- Chemistry, CEA and CA19.9 performed within 7 days from treatment start
- Coagulation (APTT & INR) performed within 7 days from treatment start
- Thyroid Function Tests (free T3, free T4 and TSH)
- Pregnancy test (urine), if applicable, performed within 7 days from treatment
- Urinalysis by dipstick
- 12-Lead electrocardiogram
- Endoscopy or upper GI imaging, to exclude patients with suspected oesophageal varices and/or gastroduodenal ulcer.
- Assessment of concomitant medications and treatments
- Assessment of ongoing symptoms/events (serious adverse events must be recorded from time of signed consent)
- Study randomisation upon completion of all screening assessments
- Baseline (screening) tumour assessments require CT/MRI (no chest x-ray) of the chest and abdomen at the minimum. If the interval between any of the baseline tumour assessments and randomisation is >28 days, the baseline tumour imaging will be repeated.

### 6.2 Study Period

Patients will receive dosing of study drug (Axitinib or placebo) as outpatients from the baseline visit. Patients will be followed up at 48-72 hours (optional), 2, 4 and 8 weeks, then monthly thereafter to a maximum of 1 year after the last patient is randomised. Clinic visits

will be performed, and haematology, clinical chemistry, urinalysis, thyroid function tests, and other safety laboratory tests, will be done as shown in the Schedule of Activities. No other chemotherapy agents will be employed during this time, however medicine to provide relief of symptoms will be allowed. Patients will undergo 8 weekly response monitoring with CT imaging as per standard RECIST evaluation v.1.1.

If significant toxicity (CTCAE Grade  $\geq 3$ ) is encountered, subsequent assessments may be performed as necessary to evaluate the specific toxicity until it resolves to baseline or CTCAE Grade  $\leq 1$ . Additional clinic visits may be required at the discretion of the investigator.

### **6.3 End of Treatment**

The study treatment may be permanently discontinued upon progression of disease, occurrence of unacceptable toxicity, withdrawal of consent, or another withdrawal criterion, unless there is sufficient evidence of clinical benefit to justify continuation of study treatment at the discretion of the investigator. However, patients who require different cancer treatment from that assigned at randomisation must be withdrawn from the study and followed as described below.

After discontinuation of study treatment and the mandated 28-day follow-up period, patients will be followed in order to collect information on further anti-tumour therapy and survival. Patients discontinuing study treatment without documented evidence of disease progression should continue tumour imaging assessments at the same frequency until disease progression, or initiation of another anticancer treatment, whichever is earlier.

The primary reason for a patient's discontinuation of the test drug will be clearly documented on the CRF. Assessments should be performed as outlined in the patient schedule above. At the end of the study or at withdrawal, the following procedures should be performed if they were not performed during the last week:

- Physical examination of major body systems, ECOG performance status, body weight, and vital signs
- Haematology, blood chemistry, coagulation tests, and urinalysis
- CT or MRI scans of chest and abdomen in addition to any other applicable sites of disease
- Assessment of adverse events. Adverse events that are serious, suspected to be related to study drug, or considered significant by the investigator must be followed after the time of therapy discontinuation until the event or its sequelae resolve or stabilise at a level acceptable to the investigator or his/her designated representative. Each serious adverse event (SAE) must be reported to the Imperial College, Pfizer, MHRA and REC
- Assessment of concomitant medications and treatments
- Assessment of Axitinib/placebo compliance/accountability

## 6.4 Subject withdrawal

When patients are permanently withdrawn from treatment, the primary reason for discontinuation must be provided. Reasons for discontinuation include:

- Death;
- unacceptable toxicity
- RECIST defined disease progression; however, patients who have progressive disease but have experienced clinical benefit from the treatment will be eligible for continued treatment provided that the treating physician has assessed the risk/benefit of taking such an approach and no alternative treatment is available.
- protocol deviation (post study start, includes subject noncompliance);
- pregnancy
- patient choice
- withdrawal of patient consent (cessation of follow-up)
- study terminated by Pfizer, Imperial College or independent safety committee

The reason for a patient's discontinuation from treatment will be documented in the end of study/withdrawal CRF. Patients will be followed for at least 28 days after the last dose of study drug for adverse events. Patients who discontinue the study prematurely will not be replaced. All efforts should be made to continue to follow a patient for survival if he/she withdrew from study treatment for reasons other than death.

Subjects may withdraw from the trial at any time at their own request, or they may be withdrawn at any time at the discretion of the investigator or sponsor for safety, behavioural, or administrative reasons. If a subject does not return for a scheduled visit, every effort should be made to contact the subject. In any circumstance, every effort should be made to document subject outcome, if possible. The investigator should inquire about the reason for withdrawal, request the subject to return all unused investigational product(s), request the subject to return for a final visit, if applicable, and follow-up with the subject regarding any unresolved adverse events.

If the subject withdraws from the trial and also withdraws consent for disclosure of future information, no further evaluations should be performed and no additional data should be collected. The sponsor may retain and continue to use any data collected before such withdrawal of consent.

## 6.5 Follow Up Visits

Patients should continue to be evaluated for 28 calendar days after the last dose of study drug (Axitinib or placebo). During the post-treatment follow-up visit, the following procedures should be performed:

- Physical examination, weight, vital signs, and ECOG
- Assessment of adverse events
- Assessment of concomitant medications and treatments

In the event a patient is unable to return to the clinic for the follow-up visit, telephone contact with the patient to assess adverse events and concomitant medications and treatments is expected. If laboratory assessments are needed to follow-up unresolved adverse events, retrieval of assessments performed at an institution local to the patient is acceptable.

The outcome of adverse events with a date of onset during the study period should be re-evaluated, and any new adverse events should be recorded. All serious adverse events, and those non-serious adverse events assessed by the investigator as possibly related to study drug should continue to be followed even after patient withdrawal from study. These adverse events should be followed until they resolve or until the investigator assesses them to be “chronic” or “stable.”

### **6.5.1. Additional Follow Up Visits**

If patient discontinues the study drug for reasons other than PD, subsequent visits may be every 8 weeks, which will include tumour assessments, until PD or a subsequent anti-cancer therapy is initiated. The following assessments should be completed:

- Tumour assessments according to the study schedule until PD.
- Recording of any new anti-cancer therapy (a tumour assessment is mandatory before initiating the new therapy).

### **6.6 Survival Follow-up**

All patients will be followed for survival every 2 months for at least 1 year after randomisation of last patient. Information regarding systemic therapy, radiation or local therapy, and surgery during survival follow up will also be collected. Premature termination of this clinical trial may occur because of a Imperial College decision, regulatory authority decision, change in opinion of the IRB/IEC, drug safety problems, or at the discretion of Pfizer. In addition, Pfizer retains the right to discontinue development of Axitinib at any time.

Regardless of the reason for termination, all data available for the patient at the time of

discontinuation of follow-up must be recorded in the CRF. All reasons for discontinuation of treatment must be documented. In terminating the study, the investigators will ensure that adequate consideration is given to the protection of the patients' interest.

## **7. Assessments**

### **7.1. Efficacy Assessment**

Baseline (screening) tumour assessments require CT/MRI (no chest x-ray) of the chest and abdomen at the minimum. If the interval between any of the baseline tumour assessments and randomisation were to become >28 days, the expired baseline tumour imaging must be repeated. At baseline, tumour lesions will be categorized as target or non-target. All patients will be evaluated for response according to RECIST version 1.1.

CT or MRI of brain at screening and subsequent imaging of brain may be performed if clinically indicated as determined by the treating physician. Bone scan at screening and subsequent imaging of bone may be performed if clinically indicated as determined by the treating physician.

For all patients, CT/MRI (covering the same anatomy as the baseline scans, except brain) will be required every 8 weeks by calendar.

Response (CR/PR) requires confirmation with CT/MRI at least 4 weeks after the response is first noted. These tumour assessments must be performed as scheduled until progression of disease or death regardless of whether patient is receiving study medication or not until permanent withdrawal from study treatment. If a patient is to start a new therapy, these tumour assessments should be repeated prior to start of the new therapy.

The same method and technique should be used to characterize each identified and reported lesion at baseline and during the study treatment period. Imaging-based evaluation over clinical examination is the required technique when both could be used to assess the anti-tumour effect of the treatment. Clinical evaluation of superficial lesions should not be used for tumour measurement. Tumour evaluation by positron emission tomography (PET) scan or by ultrasound may not substitute for CT or MRI scans.

If a patient develops new or worsening pleural effusion or ascites that is large enough for thoracentesis or paracentesis, a fluid sample should be obtained for cytological examination to determine whether the fluid collection is malignant unless there is a reasonable clinical contra-indication to do so. If fluid cytology is negative for malignant cells (defined as non-positive for presence of malignant cells, including “negative”, “atypical” or “indeterminate”), then the new or enlarging fluid collection alone should not be used as evidence of PD. If fluid cytology is positive (including “positive” or “malignant”), then “PD” will be assigned.

All patients’ files must be available for CRF source verification.

## **7.2. Physical Examination**

A complete physical examination including the assessment of all body systems (including neurological assessment), the measurement of body weight, height, heart rate, temperature, and assessment of ECOG performance status (See Appendix 2) will be performed prior to the first dose. A single 12 lead ECG should be performed on all patients at screening. If the mean QTc interval is prolonged (>500 milliseconds), then the ECG should be re-read by a cardiologist or other qualified person at the site for confirmation. Additional ECGs may be performed as clinically indicated. After the initial complete examination, targeted examinations based on signs and symptoms may be performed. All examinations must be performed by qualified health care professionals. Findings of all physical examinations should be recorded in the source documents, and any change from baseline considered by the investigator to be clinically significant should be recorded as an adverse event in the case report form.

## **7.3 Blood Pressure Assessments**

Blood pressure readings should be taken in the seated position after the patient has been sitting quietly for 5 minutes and are required at each clinic visit. All patients receiving study drug will be issued a BP measurement diary. Blood pressure readings should be taken in the seated position after the patient has been sitting quietly for 5 minutes. Patients should be instructed to inform their doctor immediately if their systolic BP rises above 140 mm Hg, diastolic BP rises above 90 mm Hg, or if they develop symptoms perceived to be related to elevated BP (e.g. headache, visual disturbance). A different home blood pressure threshold for contacting physician may be used according to the physician's clinical judgment.

## **7.4. Urinalysis**

The following urinalysis will be performed by routine laboratory test at the intervals described in the Schedule of Tests and Procedures Table: protein, glucose, and blood. Patients with 2+ proteinuria will have protein quantified by 24-hour urine protein determination.

## **7.5. Haematology**

The following haematology tests will be performed at the intervals described in the Schedule of Tests and Procedure Tables: haemoglobin (Hgb), white blood cell count (WBC), WBC differential and platelet count. For patients experiencing erythrocytosis (elevated Hgb), regular phlebotomy should be considered to maintain normal Hgb.

## **7.6. Biochemistry**

The following clinical chemistry tests will be performed at the intervals described in the Schedule of Events: creatinine, sodium (Na+), potassium (K+), chloride (Cl), calcium (Ca+), alkaline phosphatase, lactate dehydrogenase (LDH), alanine aminotransferase (ALT, or SGPT), aspartate aminotransferase (AST, or SGOT), total protein, albumin, total bilirubin, glucose, phosphate, gamma-glutamyl-transpeptidase (GGT), and AFP.

## **7.7. Thyroid Function Tests**

Serum or plasma Thyroid Function Tests (free T3, free T4 and TSH) should be performed for all randomized patients (in both study arms) at baseline (C1D1 or within 7 days of pre-dose). Subsequently TSH should be done at 2 weeks, 4 weeks and 8 weeks after starting therapy and 4 weekly thereafter until 4 weeks after the final dose. Subsequent free T3, free T4 should be performed when clinically indicated. Patients should be monitored for signs and symptoms of hypothyroidism, such as fatigue, deepening of voice, cold intolerance, constipation, anorexia, periorbital edema, myxedema, or changes in skin or hair. Hypothyroidism should be treated per standard medical practice to maintain euthyroid state.

## **7.8 Contrast Enhanced Hepatic Perfusion Index**

The contrast enhanced hepatic perfusion index will be performed as follows at baseline, 2 weeks and 8 weeks as a putative early response biomarker:

1. Patient is instructed to fast for 4 hours pre-procedure
2. CEHPI performed with patient supine using iu22 ultrasound platform, C5-1 ultrasound probe, general contrast settings (mechanical index 0.06, maximum dynamic range) and 2.4ml of intravenous SonoVue through a 20G or larger cannula or chemotherapy line.
3. Patient then takes medication with food, allowing pharmacokinetic samples to be taken using this as a trough point.

The procedure is outlined in more detail in Appendix 5.

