## 5.11 Axitinib/Placebo Dose Reduction for Hypertension

Patients treated with Axitinib/placebo will be issued blood pressure cuffs (provided by Pfizer Inc) for home monitoring and instructed to measure their blood pressure (BP) twice daily, prior to taking each dose. All blood pressure measurements will be recorded in a diary and brought to the nurse or study coordinator at each clinic visit. Patients should be instructed by the study staff to contact their physician for guidance if their systolic blood pressure rises above 140 mm Hg, diastolic blood pressure rises above 90 mm Hg, or if they develop symptoms perceived to be related to elevated BP (eg, headache, visual disturbance). See below for dose modifications for hypertension. A different blood pressure threshold for contacting physician may be used according to the physician's clinical judgment. See below for dose modifications for hypertension.

New or additional antihypertensive therapy (see Section 5.4, Concomitant Medication(s) for guidance) should be started if 2 BP readings, preferably taken in the clinic and separated by at least 1 hour, show the following: 2 systolic BP readings greater than 140 or 2 dBP readings greater than 90 mm Hg. Alternately, the dose of existing antihypertensive medication(s) may be increased. Investigator may use clinical judgment to start new or additional antihypertensive therapy at a lower blood pressure threshold. If the patient is already on maximal antihypertensive treatment, the Axitinib dose should be reduced by 1 dose level (see Table 4).

Patients who have 2 systolic BP readings, separated by at least 1 hour, greater than 160 mm Hg, or 2 dBP readings, separated by at least 1 hour, greater than 105 mm Hg, will have treatment with Axitinib/placebo held. (Note: if Axitinib/placebo is held, patients receiving antihypertensive medications should monitor closely for hypotension and restart Axitinib/placebo at one lower dose level (see Table 4) as soon as BP is <140/90 mm Hg. The plasma half-life of Axitinib is 2 – 4 hours and BP usually decreases within 1-2 days following dose interruption.)

Patients removed from treatment for intolerable toxicity should still be followed with regular tumour assessments until disease progression or start of new treatment, and for survival thereafter.

Degree of Blood Pressure Elevation			
Systolic Pressure	OR	Diastolic Pressure	Management

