## **7.9 Axitinib Pharmacokinetic Assessments**

No baseline pharmacokinetic testing is required as the value is known to be zero in those who have not received Axitinib.

On day 15 (day of CEHPI) medication will be taken after the ultrasound examination (time zero). After this blood samples will be taken at:

- 1 hour post dose
- 2 hours post dose
- 4 hours post dose

This will be repeated on day 28 and at restaging after 8 weeks at the usual clinic appointments. If there is disease progression pharmacokinetic testing will additionally be performed.

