## 9.3 Pharmacokinetic (PK) analysis

The PK's of Axitinib will be correlated with the CEPHI index. It is not currently known whether a specific level of PK is required for threshold effect on vasculature shut-down, or whether there is constant linear relationship to dose. This is the first study that may understand this better.

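### The Day 15 and week 8 scans precede the dose at what 7.8 calls the trough, but 7.9 samples only 1, 2 and 4 h after the next dose, so the concentration at the scan is not measured

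*Combined protocol and SAP*

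**What the plan says.** Section 7.8 sets the order at each scheduled CEHPI (baseline, 2 weeks, 8 weeks): a 4-hour fast, the scan, then the dose. It ends: "Patient then takes medication with food, allowing pharmacokinetic samples to be taken using this as a trough point".

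Section 7.9 gives the PK sampling. For Day 15 it says "medication will be taken after the ultrasound examination (time zero). After this blood samples will be taken at", followed by three times: "1 hour post dose", "2 hours post dose" and "4 hours post dose". The same scheme is repeated on Day 28 and at the 8-week restaging. PK is also planned at progression, without clock times. Baseline PK is omitted because the value is zero before any Axitinib has been taken.

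The Schedule of Activities and section 3 give PK visits or days only, with no clock times. Section 5.8 sets dosing about 12 hours apart, and section 5.11 states: "The plasma half-life of Axitinib is 2 – 4 hours".

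The data serve a secondary endpoint (section 2.2), whether CEHPI is a correlative biomarker of Axitinib PK. Section 9.3 says "The PK's of Axitinib will be correlated with the CEPHI index" and raises the question of a threshold level for the vascular effect. It names no PK quantity.

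**The concern.** Section 7.8 refers to a trough that 7.9 never draws. The one reason given for leaving out a sample, a known value of zero, covers untreated patients only and so does not apply at Day 15 or week 8.

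If staff follow 7.9 exactly, each scan is paired with concentrations from a tablet swallowed after the scan was finished. A threshold question is most directly addressed with the concentration present when perfusion was measured, and that value is absent. Once the visit has passed it cannot be recovered.

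Titration adds a second difficulty. Dose level is reviewed fortnightly, so Day 15 falls at a review. The documents do not say whether the post-scan dose is at the old or the new level. The three samples may therefore reflect a different dose level from the one the patient was taking when scanned.

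**Working it through.** The plan states no figure for this analysis (no power, sample size or precision), so there is nothing to reproduce. Two checks apply.

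**1. Count the samples around each scan**

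| Occasion | CEHPI | PK at or before the scan | PK after the post-scan dose |
|---|---|---|---|
| Baseline | yes | none; taken as zero | not applicable |
| 48–72 h (optional) | yes | none | none |
| Day 15 | yes | none listed | 1, 2, 4 h |
| Day 28 | no | – | 1, 2, 4 h after that day's dose |
| Week 8 | yes | none listed | 1, 2, 4 h |
| Progression | yes (section 3) | times not given | times not given |

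The gap is therefore established for Day 15 and week 8.

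**2. Can the scan-time level be inferred from the 1, 2 and 4 h samples?**

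Inputs from the documents: half-life 2–4 h (5.11) and dosing interval 12 h (5.8). Assumption, not in the documents: a one-compartment oral model with absorption rate ka of 0.5, 1 or 2 per hour. It is also assumed that the previous dose was 12 h before the scan.

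*Simple decay from 4 h to 12 h*: ratio = 2^(−8/half-life).
- Half-life 2 h: 2^(−4) = 0.0625
- Half-life 3 h: 2^(−2.67) = 0.1575
- Half-life 4 h: 2^(−2) = 0.25

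The 12 h level is about 6–25% of the 4 h level, extrapolated over 8 h, which is 2 to 4 half-lives.

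*Steady-state model*: with ke = ln 2 / half-life, the relative concentration is

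C(t) = [ka/(ka − ke)] × [e^(−ke·t)/(1 − e^(−12ke)) − e^(−ka·t)/(1 − e^(−12ka))], with C(0) = C(12).

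| Half-life | ka | C(0) | C(1) | C(2) | C(4) | C(12)/C(4) |
|---|---|---|---|---|---|---|
| 2 h | 0.5 | 0.044 | 0.359 | 0.453 | 0.386 | 0.113 |
| 2 h | 1.0 | 0.024 | 0.536 | 0.570 | 0.361 | 0.067 |
| 2 h | 2.0 | 0.019 | 0.705 | 0.592 | 0.307 | 0.063 |
| 4 h | 0.5 | 0.215 | 0.540 | 0.672 | 0.667 | 0.322 |
| 4 h | 1.0 | 0.173 | 0.717 | 0.814 | 0.669 | 0.258 |
| 4 h | 2.0 | 0.156 | 0.904 | 0.865 | 0.625 | 0.250 |

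- The pre-dose level is 6–32% of the 4 h level, about a fivefold range (0.322/0.063 = 5.1).
- The 1 h sample is a poor stand-in. It is 2.5 times (0.540/0.215) to 37 times (0.705/0.019) the pre-dose level.
- The slope between 2 h and 4 h does not rescue the estimate when absorption is slow. With half-life 4 h and ka 0.5 the two values are 0.672 and 0.667, nearly flat, although the drug is being eliminated with a 4 h half-life.
- The share of AUC(0–12) lying after the 4 h sample is 29–59% across the grid, so exposure over the whole interval is not observed either.
- The model peak falls between 1.05 and 2.84 h, inside the sampled window. Observed peak and early partial AUC are therefore reasonably covered.

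**The case against.** The strongest reply is that 9.3 promises no correlation with the concentration at the moment of the scan. The background section describes vascular change over days to weeks, and CEHPI is read after two weeks of continuous dosing. Peak or early exposure may matter as much as trough, and the documents do not settle it. The 1–4 h window captures the peak, so a PK–CEHPI correlation can be carried out. This stands, and it limits the point: the endpoint is weakened, not lost. It also shows a gap of its own, since 9.3 names no exposure measure at all.

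Other limits stand too. The word trough is the protocol's label: only a 4-hour fast is required, and neither 7.8 nor 7.9 fixes or records the time of the previous dose relative to the scan. Section 7.8 may have intended a sample that 7.9 omitted, or may simply use the dose as a time reference. Either way the two sections need reconciling.

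A reader might infer three stronger things that the documents do not support:
- *That the scan-time level is never measured.* Baseline is taken as zero, and PK at progression has no clock times, so its absence there cannot be shown.
- *That the PK–CEHPI and threshold questions cannot be answered.* Observed peak and partial AUC remain usable.
- *That trough relative to peak varies about tenfold between patients.* The model's trough/peak ratio does run from 0.03 to 0.31, but that spans a grid of assumed parameters and is not observed variation. At any one absorption rate the range is 3.2- to 6.2-fold.

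**Conclusion.** The concern holds for Day 15 and week 8. Followed as written, the plan leaves the concentration at the scan undrawn, although 7.8 refers to a trough, and pairs each scan with values from a later dose. The listed samples leave the missing level uncertain by a factor of about 4 (simple decay, 6–25% of the 4 h level) to 5 (steady-state model, 6–32%). The first range rests on the protocol's half-life and a full 12 h since the previous dose. The second also rests on the assumed absorption rates.

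The consequence is confined to the PK–CEHPI secondary endpoint and the threshold question in 9.3. The primary PFS analysis, the CEHPI–PFS comparison, overall survival and safety are untouched. This is a cheap improvement worth making, not a flaw that undermines the trial.

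**What to change.** 1. **Section 7.9 and the Schedule of Activities:** add a time-zero (pre-dose) 3 ml sample at the Day 15 and week 8 CEHPI, through the access already placed for the contrast agent. Align 7.8 with this.
2. **CRF:** record the time and dose level of the previous dose, and the dose level taken after the scan.
3. **Section 9.3:** name the measured pre-dose concentration as an exposure measure to correlate with CEHPI change, alongside observed peak or partial AUC(0–4).
4. **AUC(0–12):** use the pre-dose value as the 12 h value only where the dose level was unchanged and the previous dose was about 12 h earlier. Otherwise the calculation can join two dose levels in one AUC.

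Cost: 50 patients × 2 occasions gives at most about 100 extra tubes. Section 7.9.1 provides for analysis of active-arm samples only, so about 33 × 2 = 66 need assay. No new visit or procedure is required, and handling is already specified in 7.9.1. A small protocol amendment is needed.
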